6.1.3.1 Laboratory Safety Evaluations (Hematology, Chemistry and Urinalysis)

Laboratory tests for hematology, chemistry, and urinalysis are specified in Appendix 2.

6.1.3.2 Pregnancy Testing

All women who are being considered for participation in the study, and who are not surgically sterilized or postmenopausal, must be tested for pregnancy within 72 hours or the first dose of study intervention. Participants must be excluded/discontinued from the study in the event of a positive test result. Repeated pregnancy test (such as monthly testing) may be conducted if required by local regulation.

6.1.4 Tumor Imaging and Assessment of Disease

Tumor imaging is strongly preferred to be acquired by computed tomography (CT). For the abdomen and pelvis, contrast-enhanced magnetic resonance imaging (MRI) may be used when CT with iodinated contrast is contraindicated, or when local practice mandates it. MRI is the strongly preferred modality for imaging the brain. The same imaging technique regarding modality, ideally the same scanner, and the use of contrast should be used in a participant throughout the study to optimize the reproducibility of the assessment of existing and new tumor burden and improve the accuracy of the assessment of response or progression based on imaging.

Brain imaging is required for all participants at screening. MRI is preferred; however, CT imaging will be acceptable, if MRI is medically contraindicated. Participant eligibility will be determined using local assessment (Investigator assessment) based on RECIST 1.1. In addition, images (including via other modalities) that are obtained at an unscheduled time point to determine disease progression, as well as imaging obtained for other reasons, but which demonstrate radiologic progression, should also be used to determine progression.

When the Investigator identifies radiographic progression per RECIST 1.1, efforts should be made to verify radiologic PD. Treatment should continue until PD has been verified. Regardless of whether PD is verified, if the Investigator considers the participant has progressed, but elects to implement iRECIST, the Investigator will assess for confirmation of progression by iRECIST at subsequent time points.

6.1.4.1 Initial Tumor Imaging

Initial tumor imaging at Screening must be performed within 30 days prior to the date of allocation. The site study team must review screening images to confirm the participant has measurable disease per RECIST 1.1.

Tumor imaging performed as part of routine clinical management is acceptable for use as screening tumor imaging if they are of diagnostic quality and performed within 30 days prior to C1D1.

Brain imaging is required to rule out radiographically detectable brain metastases. Magnetic resonance imaging is preferred; however, CT imaging will be acceptable, if MRI is medically contraindicated or CT is mandated by local practice.

6.1.4.2 Tumor Imaging During the Study

The first on-study imaging assessment should be performed at 9 weeks (\pm 7 days) from the date of allocation. Subsequent tumor imaging should be performed every 9 weeks (\pm 7 days) or more frequently if clinically indicated. After 1 year (\pm 7 days), participants who remain on treatment will have imaging performed every 12 weeks (\pm 7 days). Imaging timing should follow calendar days and should not be adjusted for delays in cycle starts. Imaging should continue to be performed until disease progression is identified by the Investigator.

Objective response should be confirmed by a repeat imaging assessment. Tumor imaging to confirm PR or CR should be performed at least 4 weeks after the first indication of a response is observed. Participants will then return to regular scheduled imaging every 9 weeks, starting with the next scheduled imaging time point. Participants who receive additional imaging for confirmation do not need to undergo the next scheduled tumor imaging if it is less than 4 weeks later; tumor imaging may resume at the subsequent scheduled imaging time point.

Confidential

Per iRECIST (Section 6.1.4.6), disease progression should be confirmed by the site 4 to 8 weeks after first radiologic evidence of PD in clinically stable participants. Participants who have unconfirmed disease progression may continue on treatment at the discretion of the investigator until progression is confirmed by the site provided they have met the conditions detailed in Section 6.1.4.6. Participants who receive confirmatory imaging do not need to undergo the next scheduled tumor imaging if it is less than 4 weeks later; tumor imaging may resume at the subsequent scheduled imaging time point, if clinically stable. Participants who have confirmed disease progression by iRECIST, as assessed by the site, will discontinue study treatment. Exceptions are detailed in Section 6.1.4.5.

6.1.4.3 End of Treatment and Follow-up Tumor Imaging

In participants who discontinue study treatment, tumor imaging should be performed at the time of treatment discontinuation (\pm 4 week window). If previous imaging was obtained within 4 weeks prior to the date of discontinuation, then imaging at treatment discontinuation is not mandatory. In participants who discontinue study treatment due to documented disease progression and the investigator elects not to implement iRECIST, this is the final required tumor imaging.

For participants who discontinue study treatment without documented disease progression, every effort should be made to continue monitoring their disease status by tumor imaging using the same imaging schedule used while on treatment (every 9 weeks in Year 1 or every 12 weeks after Year 1) to monitor disease status until the start of a new anticancer treatment, disease progression, pregnancy, death, withdrawal of consent, or the end of the study, whichever occurs first.

6.1.4.4 RECIST 1.1 Assessment of Disease

RECIST 1.1 will be used as the primary measure for assessment of tumor response, date of disease progression, and as a basis for all protocol guidelines related to disease status (eg, discontinuation of study treatment). Although RECIST 1.1 references a maximum of 5 target lesions in total and 2 per organ, the Sponsor allows a maximum of 10 target lesions in total and 5 per organ, if clinically relevant to enable a broader sampling of tumor burden. The first half of the flowchart in [Figure 2] illustrates the imaging flow involving verification of PD for clinically stable participants.

6.1.4.5 iRECIST Assessment of Disease

iRECIST is based on RECIST 1.1, but adapted to account for the unique tumor response seen with immunotherapeutic drugs. iRECIST will be used by the investigator to assess tumor response and progression and make treatment decisions. When clinically stable, participants should not be discontinued until progression is confirmed by the investigator, working with local radiology, according to the rules outlined in Appendix 4. This allowance to continue treatment despite initial radiologic disease progression takes into account the observation that some participants can have

a transient tumor flare in the first few months after the start of immunotherapy, and then experience subsequent disease response. This data will be captured in the clinical database.

Clinical stability is defined as the following:

- Absence of symptoms and signs indicating clinically significant progression of disease
- No decline in ECOG performance status
- No requirements for intensified management, including increased analgesia, radiation, or other palliative care

Any participant deemed clinically unstable should be discontinued from study intervention at central verification of site-assessed first radiologic evidence of disease progression, and is not required to have repeat tumor imaging for confirmation of disease progression by iRECIST.

If the investigator decides to continue treatment, the participant may continue to receive study intervention and the tumor assessment should be repeated 4 to 8 weeks later to confirm disease progression by iRECIST, per investigator assessment. Images should continue to be sent in to the iCRO for potential retrospective BICR.

If repeat imaging does not confirm disease progression per iRECIST, as assessed by the investigator, and the participant continues to be clinically stable, study intervention may continue and follow the regular imaging schedule. If disease progression is confirmed, participants will be discontinued from study intervention.

If a participant has confirmed radiographic progression (iCPD) as defined in Appendix 4, study intervention should be discontinued; however, if the participant is achieving a clinically meaningful benefit, an exception to continue study intervention may be considered following consultation with the Sponsor. In this case, if study intervention is continued, tumor imaging should continue to be performed following the intervals as outlined in Section 6 and submitted to the iCRO.

A description of the adaptations and iRECIST process is provided in Appendix 4. A summary of imaging and treatment requirements after first radiologic evidence of progression is provided in Table 6 and illustrated as a flowchart in Figures 1 and 2.

Table 6 Imaging and Treatment After First Radiologic Evidence of Progressive Disease

any Stable		Clinically Unstable	
ng	Treatment	Imaging	Treatment
imaging 8 weeks to n disease ssion	May continue study treatment at the assessment of the investigator and after the participant's consent	Repeat imaging at 4 to 8 weeks to confirm disease progression per investigator's discretion only.	Discontinue treatment
imaging 8 weeks to n disease ssion.	May continue study intervention at the investigator's discretion while Awaiting confirmatory tumor imaging by site by iRECIST.	Repeat imaging at 4 to 8 weeks to confirm disease progression per investigator's discretion only.	Discontinue treatment
litional g required.	Discontinue treatment (exception is possible upon consultation with Sponsor).	No additional imaging required.	Not applicable
imaging 8 weeks to n disease ssion. May at next ly led g visit.	Continue study intervention at the investigator's discretion.	Repeat imaging at 4 to 8 weeks to confirm disease progression per investigator's discretion only.	Discontinue treatment
ue ly led g nents.	Continue study intervention at the investigator's discretion.	Continue regularly scheduled imaging assessments.	May restart study intervention if condition has improved and/or clinically stable per investigator's discretion. Next tumor imaging should occur

6.1.5 Tumor Tissue Collection and Correlative Studies Blood Sampling

Tumor tissue and blood specimens will be collected and banked for correlative research studies. An additional optional collection for specimen banking will be collected for those who consent for at least 15 subjects (in no certain order). Fresh tumor biopsy samples will be collected prior to initiating treatment. Archival tissue may be used in place of pre-treatment biopsy. A second biopsy will be collected on cycle 3 day 8 (+/- 1 day). Blood specimens including the optional specimen banking samples will be collected during screening and on day 1 of cycles 1-6.

Correlative and optional specimen banking samples collected for Screening may be used for C1D1 if the collection is within 3 days prior to C1D1.

6.1.6 Other Procedures

6.1.6.1 Discontinuation and withdrawal

Participants who discontinue study intervention prior to completion of the treatment period should be Confidential

Protocol 2021000802 MISP 60931 Version Date: 30Jul2024

encouraged to continue to be followed for all remaining study visits as outlined in the SoA and Section 6.2.

Participants who withdraw from the study should be encouraged to complete all applicable activities scheduled for the final study visit at the time of withdrawal. Any AEs that are present at the time of withdrawal should be followed in accordance with the safety requirements outlined in Section 6.2.

6.1.7 Visit Requirements

Visit requirements are outlined in Section 2.3 – Schedule of Activities. Specific procedure-related details are provided above in Section 6.1 - Trial Procedures.

6.1.7.1 Screening

6.1.7.1.1 Screening Period

Please reference schedule of activities in section 2.3.

6.1.7.2 Treatment Period

Please reference schedule of activities in section 2.3

6.1.7.3 **Post-Treatment Visits**

6.1.7.3.1 Safety Follow-Up Visit

The mandatory Safety Follow-Up Visit should be conducted approximately 30 days after the last dose of study intervention or before the initiation of a new anti-cancer treatment, whichever comes first.

6.1.7.3.2 Efficacy Follow-up Visits

Participants who complete the protocol-required cycles of study intervention of who discontinue study intervention for a reason other than disease progression will begin the Efficacy Follow-Up Phase and should be assessed every 6 weeks (42 ± 7 days) by radiologic imaging to monitor disease status. After 1 year, the imaging time point will occur every 9 weeks (± 7 days). Every effort should be made to collect information regarding disease status until the start of new anti-cancer therapy, disease progression, death, end of the study or if the participant begins retreatment with pembrolizumab as detailed in Section 5.2.3. Information regarding post-study anti-cancer treatment will be collected if new treatment is initiated. Participants who completed all efficacy assessments and/or will not have further efficacy assessments must enter the Survival Follow-up Phase.

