1.0 TRIAL SUMMARY

Abbreviated Title	Lenvatinib plus pembrolizumab in patients with immune checkpoint inhibitor naïve metastatic uveal melanoma
Trial Phase	Phase II
Clinical Indication	Treatment of participants with immune checkpoint inhibitor naïve metastatic uveal melanoma
Trial Type	Interventional
Type of control	n/a
Route of administration	Oral and IV
Treatment Groups	Single arm: Lenvatinib 20 mg daily plus pembrolizumab 200 mg IV every 3 weeks.
Number of trial participants	30
Estimated enrollment period	20 months
Estimated duration of trial	48 months (FPFV to LPLV)
Duration of Participation	Subjects will participate in the clinical trial from the time of signing the ICF until the final protocol specified contact. Subjects who discontinue treatment for reasons other than disease progression or treatment related toxicity will have post-treatment follow-up until documented radiographic evidence of disease progression (per iRECIST), initiation of a subsequent anti-cancer therapy, death, pregnancy, withdrawal of consent, lost to follow up or the end of the clinical trial.
Estimated average length of treatment per patient	6 months

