3.0 OBJECTIVE(S), HYPOTHESIS(ES), AND ENDPOINT(S)

3.1 **Primary Objective(s), Hypothesis(es), and Endpoint(s)**

(1) **Objective:** To evaluate the effect of lenvatinib + pembrolizumab on progression free survival.

Hypothesis: Treatment with Lenvatinib + pembrolizumab will result in improved progression free survival as compared with previously reported systemic therapies including pembrolizumab monotherapy, ipilimumab + nivolumab and tebentafusp.

Primary Endpoint: Progression free survival, defined as the time from enrollment to the first documented evidence of disease progression or death.

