5.4 Participant Discontinuation Criteria

Discontinuation of study intervention does not represent withdrawal from the study.

As certain data on clinical events beyond study intervention discontinuation may be important to the study, they must be collected through the participant's last scheduled follow-up, even if the participant has discontinued study intervention. Therefore, all participants who discontinue study intervention prior to completion of the protocol-specified treatment period will still continue to be monitored in this study and participate in the study visits and procedures as specified in Section 2.3 unless the participant has withdrawn from the study (Section 5.5).

Participants may discontinue study intervention at any time for any reason or be discontinued from the study intervention at the discretion of the investigator should any untoward effect occur. In addition, a participant may be discontinued from study intervention by the investigator or the Sponsor if study intervention is inappropriate, the study plan is violated, or for administrative and/or other safety reasons.

A participant must be discontinued from study treatment but continue to be monitored in the study for any of the following reasons:

- The participant or participant's legally acceptable representative requests to discontinue study intervention
- After prolonged study intervention interruption that prohibits restarting study intervention if agreed upon with the Sponsor
- Radiographic disease progression outlined in Section 6.1.4.
- Any progression or recurrence of any malignancy, or any occurrence of another malignancy that requires active treatment
- Any study intervention-related toxicity specified as a reason for permanent discontinuation as defined in the guidelines for dose modification due to AEs in Section 5.2.2.
- The participant has a medical condition or personal circumstance which, in the opinion of the investigator and/or sponsor, placed the participant at unnecessary risk from continued administration of study treatment.
- The participant has a confirmed positive serum pregnancy test

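### The follow-up sections disagree on who keeps being scanned after a stop for progression that does not meet RECIST 1.1, and the plan does not say how such a patient counts in PFS

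*Combined protocol and SAP*

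**What the plan says.** - **Entry to efficacy follow-up (6.1.7.3.2).** Apart from those who complete treatment, it covers patients who "discontinue study intervention for a reason other than disease progression will begin the Efficacy Follow-Up Phase". They "should be assessed every 6 weeks (42 ± 7 days) by radiologic imaging to monitor disease status", then every 9 weeks after one year. Patients with no further efficacy assessments go to survival follow-up, which Section 6.1.7.3.3 sets at 12-weekly contacts.
- **Imaging after discontinuation (6.1.4.3).** "For participants who discontinue study treatment without documented disease progression, every effort should be made to continue monitoring their disease status", every 9 weeks in Year 1 and every 12 weeks after. A scan at discontinuation (± 4 weeks) is also asked for, unless one was done in the previous 4 weeks.
- **Trial Summary (1.0).** A third wording: it leaves out stops for progression and for treatment-related toxicity, and ends follow-up at radiographic progression per iRECIST.
- **Reasons for stopping (5.4).** Radiographic progression is one item. A separate item reads "Any progression or recurrence of any malignancy, or any occurrence of another malignancy that requires active treatment".
- **Primary endpoint (3.1).** PFS is "the time from enrollment to the first documented evidence of disease progression or death", with no criteria named.
- **Dating of progression (6.1.4.4).** "RECIST 1.1 will be used as the primary measure for assessment of tumor response, date of disease progression".
- **Statistical section (7.2).** It gives no PFS event or censoring rules. Enrollment stops at the 15-patient interim if ORR is below 20% or median PFS is below 6 months.

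**The concern.** Section 6.1.7.3.2 selects patients by the reason for stopping, and Section 6.1.4.3 by what has been documented. The two part company for a patient whom the investigator stops for progression when no scan meets RECIST 1.1. Read literally, 6.1.7.3.2 schedules no more efficacy scans for that patient.

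Such patients are likely to be doing badly. If their scans end without a radiographic event, their PFS time either runs on to death or is censored at a point related to prognosis. Both inflate PFS. The bias falls on the primary endpoint, which will be read against historical medians of 3.5 months (PD-1 inhibitors, Section 7.2) and 5.5 months (ipilimumab plus nivolumab, Section 4.1). It also falls on the 6-month PFS arm of the interim rule.

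**Working it through.** **The plan's own figure.** The only design calculation is ORR power. A normal approximation gives 0.554, 0.776 and 0.906 against the stated 0.55, 0.78 and 0.91, so it reproduces. It does not involve PFS, so the size of this point has to be illustrated.

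**Inputs from the documents.** 9-weekly scans, so the first three fall at 2.07, 4.14 and 6.21 months; historical median 3.5 months; interim threshold 6 months in 15 patients; historical ORR 10%.

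**Assumptions not in the documents.** Exponential time to progression, median 3.5 months (rate a = ln 2/3.5 = 0.198). Exponential survival after progression, median 10 months (b = ln 2/10 = 0.0693). A share f = 10–20% of progressions is clinical-only. Full follow-up.

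**Step 1. Chance of PFS beyond 6 months for each kind of patient.**
- Event on the clinical stop date: exp(−6a) = 0.305.
- Event at death: [a·exp(−6b) − b·exp(−6a)]/(a − b) = 0.851.
- Radiographic progression, seen at the next scan: the patient must progress after the 4.14-month scan, probability exp(−4.14a) = 0.441. Subtract 0.009 for those who progress after it and die before 6 months. Result 0.432.

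**Step 2. Mix the groups.**
- f = 20%, event at stop: 0.8 × 0.432 + 0.2 × 0.305 = 0.41. Event at death: 0.8 × 0.432 + 0.2 × 0.851 = 0.52.
- f = 10%: 0.9 × 0.432 + 0.1 × 0.305 = 0.42, against 0.9 × 0.432 + 0.1 × 0.851 = 0.47.
- With 5-month survival after progression and f = 20%: 0.40 against 0.49.

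**Step 3. Chance that the 15-patient median is below 6 months.** This is the chance that at least 8 of 15 patients have PFS of 6 months or less, that is P(Bin(15, 1 − S) ≥ 8), where S is the figure from Step 2.

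| Setting (10-month survival after progression) | Event at stop | Alternative |
|---|---|---|
| f = 10%, none caught by a scan | 0.74 | 0.58 |
| f = 20%, none caught | 0.77 | 0.45 (0.46 in one simulation) |
| f = 20%, half caught at stopping | 0.77 | 0.62 |
| f = 20%, 80% caught at stopping | 0.77 | 0.72 |
| All kept on 9-weekly scans | 0.77 (f = 20%) | 0.71 |

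**Step 4. The whole interim rule.** At a true ORR of 10%, P(2 or fewer responses in 15) = 0.816. Assuming independence, the chance of stopping is 1 − 0.184 × (1 − 0.77) = 0.96 when the stop is the event. In the worst case it is 1 − 0.184 × (1 − 0.45) = 0.90.

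**Step 5. Why the median is a poor summary.** The modelled median sits at 4.14 or 6.21 months, according to which side of 50% the curve lies between those scans. At f = 20% with none caught it crosses from 4.1 to 6.2 months. At f = 10% it does not move. A cross-check without a scan grid (f = 20%, 4 months from stop to death, true median 3.5 months) moves the median only from 3.5 to about 4.35 months.

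**Step 6. Censoring instead of death.** In the scan-grid simulation, censoring clinical-only patients at the last scan leaves 46–50% beyond 6 months, also above the 41–42% in Step 2.

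**The case against.** The strongest reply is that the documents already settle this. Section 6.1.4.4 makes RECIST 1.1 the basis for all guidance on disease status, so progression in 6.1.7.3.2 can be read as RECIST progression. A clinical-only stop is then a stop for another reason, and the two sections agree on who is scanned. Section 6.1.7.3.2 never mentions clinical progression. The Section 5.4 item may be aimed partly at other cancers, and where the protocol discusses clinical instability it ties stopping to first radiologic progression.

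That reading is available but not secure. The Trial Summary uses plain progression for the reason for stopping and radiographic progression for the end of follow-up, in one sentence. Section 6.1.4.5 also gives iRECIST a role in assessing progression and in treatment decisions.

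A reader might infer that death is the only event left, so that PFS equals OS for these patients. The documents do not support that. Section 6.1.4.3 asks for a discontinuation scan. Section 6.1.4 lets unscheduled images, and images taken for other reasons, establish progression. Sections 5.4 and 6.1.6.1 continue study visits after discontinuation. These routes will catch some patients, though a discontinuation scan may be waived or may not meet RECIST 1.1.

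**Conclusion.** The conflict in wording is real, and the scoring of these patients is unstated. The likely direction of bias in PFS is upward. The size is unknown because no rate of clinical-only stops is given. Under the assumptions above, the worst case adds about 5 to 11 percentage points to PFS beyond 6 months and takes 0.16 to 0.32 off the chance that the PFS arm stops the trial. With 80% of such patients caught, at a 20% clinical-only share, that chance falls only from 0.77 to 0.72.

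Two stronger conclusions are tempting and should not be drawn. The 4.1 to 6.2 month shift in the median is not an expected bias: it needs 20% clinical-only progression with none caught, and it largely reflects the 9-week grid. Nor is the interim rule disabled: its ORR arm holds overall stopping at about 0.90 even in the worst case. Full follow-up is also assumed, whereas the interim can be triggered soon after first restaging.

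This should be corrected, because the change is cheap and removes an informative loss of scans from the primary endpoint.

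**What to change.** 1. In 6.1.7.3.2 and the Trial Summary, adopt the 6.1.4.3 criterion, worded as stopping without documented radiographic progression.
2. In 3.1, state that the primary PFS event is radiographic progression dated by RECIST 1.1, as in 6.1.4.4, or death. Reconcile this with the iRECIST wording in the Trial Summary.
3. Record clinical and radiographic progression separately on the CRF.
4. Add to Section 7 a sensitivity analysis that counts a stop for clinical progression as an event on the stop date.
5. In the same edit, reconcile the follow-up scan intervals. Section 6.1.7.3.2 and the efficacy follow-up column of the Schedule of Activities give 6 then 9 weeks. Section 6.1.4.3 and the imaging note in that Schedule give 9 then 12 weeks. Changing the entry wording alone would leave this contradiction in place.

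The cost is one CRF field, one extra analysis and some rewording. A few patients stay on scans that 6.1.4.3 already requests, and PFS may look slightly shorter.
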